8.7. Secondary objectives

The secondary objectives are descriptive with no performance requirements and no sample size has been calculated.

8.7.1. Secondary objective: Intuitiveness of AirWaze Features

Objective

To assess intuitiveness of the individual AirWaze features by the physicians.

Endpoint

Semi-structured questionnaire to assess intuitiveness of AirWaze features for CBCT-guided biopsy of peripheral pulmonary nodules.

Analysis

The results will be analysed by using the average intuitiveness scores per feature and the intuitiveness score development in time per feature. The intuitiveness of the AirWaze features is indicated as sufficient when the average score per AirWaze feature equals or is higher than 4 (= agree). No statistical test will be performed due to limited data points. More information on the intuitiveness questionnaire can be found in Appendix III: Semi-structured Questionnaires – Assessment of the intuitiveness of AirWaze features.

IGT Systems	Feasibility Clinical Investigation Protocol	Doc ID: XCY607-130895 Rev: 04
	AirWaze – easy and advanced tools for CBCT guided lung interventions	Date: 2024-Jun-19 Page 27 of 56

8.7.2. Secondary objective: Quantitative and qualitative assessment of developed algorithms

Objective

The objective is to assess the performance of the developed AirWaze algorithms. These algorithms are: (i) the segmentation of the bronchial tree based on the pre-procedural CT; (ii) the elastic registration of the pre-procedural CT scan (including segmentations) to the intraoperative CBCT scan(s), and (iii) the automatic device detection on the intraoperative CBCT scans.

Endpoint

Quantitative and qualitative assessment of developed algorithms endpoints:

- The quality of the segmented bronchial tree is defined on a 5-point Likert scale. The segmentation of the bronchial tree is rated independently from the location of the lesion. The segmentation is rated with a Likert score 1 = only trachea, right/left main bronchus, and bronchus intermedius are segmented, to, Likert score 5 = Bronchioles on a distance < 2 cm from the pleura are segmented.
- The quality of the image registration is defined on a 5-point Likert scale from 1 (bad) to 5 (excellent). The image registration is bad if the registration around the target of interest shows large errors. The image registration is excellent if the images are registered accurately around the target of interest.
- The quality of the automatic device detection is defined on a 5-point Likert scale from 1 (bad) to 5 (excellent). The automatic device detection is poor if the device is barely or wrongly detected. The automatic device detection is excellent if the device is detected completely.
- Algorithm failures are defined as the percentage of algorithm failures and the ability to quickly correct/work around them related to 1) segmentation of bronchial tree on preoperative CT scan, 2) image registration of the preoperative CT scan to the intraoperative CBCT and/or CBCT-FS scans or between CBCT(-FS) scans and 3) automatic catheter detection on both CBCT and CBCT-FS.

Analysis

The objective related to the clinical and technical feasibility of CBCT-FS will be evaluated by calculating:

- Quality of the segmented bronchial tree is considered sufficient when the average Likert score equals or is higher than 4. For this categorical variable, counts and percentages will be calculated as well.
- Quality of the image registration is considered sufficient when the average Likert score equals or is higher than 4. For this categorical variable, counts and percentages will be calculated as well.
- Quality of the automatic device detection is considered sufficient when the average Likert score equals or is higher than 4. For this categorical variable, counts and percentages will be calculated as well.
- Algorithm failures are acceptable when in <5 % of the cases for pulmonary lesions algorithm failures related to CBCT or CBCT-FS occurred.

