7.1.1. Endpoints

The primary and secondary endpoints are based on the objectives (Section 6) and are described below.

Primary endpoints

The system usability will be assessed by using the System Usability Scale (SUS) ¹⁵. An average SUS of greater than 70 will indicate a good usability design of the AirWaze Software solution. The SUS will be measured per operator every 4 procedures.

Image-based tool-in-lesion confirmation accuracy of CBCT-FS is defined as the number of procedures where CBCT-FS scans were adequate to define tool-in-lesion compared to conventional CBCT scans (gold-standard). The image-based tool-in-lesion accuracy is defined as the sum of the number of tool-in-lesion in both the CBCT-FS and CBCT images (i.e. true positives), and the number of no tool-in-lesion confirmation in both the CBCT-FS and CBCT images (i.e. true negatives), divided by the total number of CBCT-FS and CBCT pairs. Image based tool-in-lesion confirmation accuracy of 90% will indicate that the CBCT-FS is postulated to be sufficient for navigation bronchoscopy.

IGT Systems	Feasibility Clinical Investigation Protocol AirWaze – easy and advanced tools for CBCT guided lung interventions	Doc ID: XCY607-130895 Rev: 04 Date: 2024-Jun-19 Page 20 of 56
-------------	--	--

Secondary endpoints

The secondary endpoints of this feasibility clinical investigation are:

- Semi-structured questionnaires to assess intuitiveness of AirWaze features for CBCT-guided biopsy of peripheral pulmonary nodules (Appendix III).
- Quantitative and qualitative assessment of the developed algorithms is assessed through a questionnaire (Appendix IV).
 - (a) Segmentation bronchial tree on pre-procedural CT.
 - (b) Elastic registration of the intraoperative CBCT scans with preprocedural CT scan.
 - (c) Automatic device detection on intraoperative CBCT scans.
- The quality of the interventional planning is defined by comparing the pre-procedural planned navigation trajectory compared to the actual navigation trajectory towards the first lesion (Appendix V).
- Confidence levels of pulmonologists are defined as a score (0-10) to examine the degree of confidence of specialists regarding: (i) the localization of the lesion and planned navigation trajectory; (ii) reaching the first pulmonary lesion based on the planning (Appendix V).

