8.2. Sample Size Justification

A total of 37 patients will be included in this feasibility study. The physicians are familiar with the AirWaze investigational device in a non-clinical setting. The clinical setting will function as clinical and technical de-risking of the software program and the information from this study will be used to design a robust pivotal claim-driven study. Semi-structured questionnaires will be used to assess the overall system usability and the accuracy of the AirWaze CBCT-FS scan. Furthermore, the number of imaging and algorithm failures and the ability to work around quickly will be evaluated. Taking into account a 10% drop-out rate, it is expected by experts that a Per Protocol population of 33 patients is sufficient to de-risk the AirWaze features.

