Appendix IV: Semi-structured Questionnaire for quantitative and qualitative assessment of the developed algorithms

The quality of the algorithms will be assessed through this questionnaire and will be conducted after every procedure per operator.

Advanced planning software

The advanced planning software contains two major algorithms for: 1) segmentation of the bronchial tree, and 2) image registration.

1. Segmentation of the bronchial tree

The segmentation of the bronchial tree is rated independently from the location of the lesion.

- **1:** Only the trachea, right/left main bronchus, and bronchus intermedius are segmented.
- **2:** RB1 t/m RB10 and LB1 t/m LB10 are segmented.
- **3:** Few (1-2) branches beyond the RB or LB branches are segmented.
- **4:** More (≥ 3) branches beyond the RB or LB branches are segmented to 2 cm from the pleura.
- **5:** Bronchioles on a distance < 2 cm from the pleura are segmented.

a. Please rate the quality of the segmented bronchial tree on the preoperative CT scan:

1	2	3	4	5	Segmentation failed
Please elaborate:					

b. Based on the segmentation of the bronchial tree, is there a bronchus sign?

- a. Yes, there is a bronchus sign.
- b. No, there is no bronchus sign.
- c. Cannot be determined, because insufficient level of bronchial tree segmentation.

c. If not sufficient level of bronchial tree segmentation: Do you have any clue what was the origin of the unacceptable segmentation?

.....

d. Did you notice/experience any glitches? If yes, please elaborate.

.....

IGT Systems	Feasibility Clinical Investigation Protocol	Doc ID: XCY607-130895
	AirWaze – easy and advanced tools for CBCT guided lung interventions	Rev: 04 Date: 2024-Jun-19 Page 46 of 56

2. Image registration

The image registration is bad if the registration around the target of interest shows large errors. The image registration is excellent if the images are registered accurately around the target of interest.

The image registration is evaluated between the different CBCT-scans made during the procedure. The most recent acquired image is the fixed image, and the older acquired image is the moving image. In future AirWaze implementation, it is desirable to replace the CBCT with the low-dose CBCT-FS. In those procedures one normal-dose CBCT is acquired. The navigation trajectory and lesion segmentations are moved from the CBCT image to the CBCT-FS images. If there are less CBCT(-FS) performed, the image registration is addressed as N/A.

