- a. Please rate the quality of the image registration at the location of the lesion:

Image registration between moved and fixed scans	1 Bad	2 Poor	3 Fair	4 Good	5 Excellent	Image registration failed
Pre-op CT --> CBCT1						
CBCT1 --> CBCT-FS1						
..... -->						
..... -->						
..... -->						

- b. If not acceptable level of image registration: Can it be corrected manually? And do you have any clue for the origin of the unacceptable levels of image registration?

.....

- c. Did you notice/experience any glitches?

.....

Automatic device detection

The automatic device detection is poor if the device is barely or wrongly detected. The automatic device detection is excellent if the device is detected completely.

1. Please rate the quality of the automatic catheter detection during the procedure after acquiring a CBCT scan:

Scan	1 Bad	2 Poor	3 Fair	4 Good	5 Excellent	Automatic device detection failed
CBCT1						
CBCT-FS1						
.....						
.....						
.....						

IGT Systems	Feasibility Clinical Investigation Protocol AirWaze – easy and advanced tools for CBCT guided lung interventions	Doc ID: XCY607-130895 Rev: 04 Date: 2024-Jun-19 Page 47 of 56
-------------	--	--

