2. If not acceptable level of automatic device detection. What is in your view the origin of the unacceptable levels of automatic device detection?

.....

3. Did you notice/experience any glitches? If yes, please elaborate.

.....

IGT Systems	Feasibility Clinical Investigation Protocol AirWaze – easy and advanced tools for CBCT guided lung interventions	Doc ID: XCY607-130895 Rev: 04 Date: 2024-Jun-19 Page 48 of 56
-------------	--	--

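### The form named as the source for the algorithm-failure endpoint does not systematically collect whether failures were corrected, or how quickly

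*Combined protocol and SAP*

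**What the plan says.** Section 8.7.2 (Endpoint, fourth bullet) gives the failure endpoint two components: "the percentage of algorithm failures and the ability to quickly correct/work around them". It applies both to three algorithms: segmentation on the preoperative CT, registration between scans, and catheter detection on CBCT and CBCT-FS. Section 8.2 repeats the second component, stating that "the number of imaging and algorithm failures and the ability to work around quickly will be evaluated".

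Section 7.1.1 names the instrument: "Quantitative and qualitative assessment of the developed algorithms is assessed through a questionnaire (Appendix IV"). Appendix IV is completed after every procedure, and section 9 allows it to be entered directly in the e-CRF as source data.

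The Analysis part of 8.7.2 has one rule for failures: "Algorithm failures are acceptable when in <5 % of the cases for pulmonary lesions algorithm failures related to CBCT or CBCT-FS occurred". It does not mention correction or work-around.

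**The concern.** An endpoint component can be reported only if some instrument asks for it. Here the text promises information on correction and speed for three algorithms, while the form's follow-up questions are mostly about cause. If that is right, the clinical study report cannot say consistently which failures were resolved on the spot and which ended use of the tool.

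This matters because section 8.2 presents the study as clinical and technical de-risking ahead of a pivotal study. A failure put right in a minute and one that made a feature unusable both enter the failure percentage as one failure. The second component of the endpoint is what would separate them.

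**Working it through.** No figure in the plan is in dispute, so the check sets the endpoint's components against the items on the form.

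**Step 1. Components required by 8.7.2, for each of three algorithms:** (a) whether it failed; (b) whether the failure was corrected or worked around; (c) whether that was quick.

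**Step 2. Items in Appendix IV.**

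| Algorithm | Failure option | Follow-up to a poor result | Correction or work-around achieved? | Time or speed? |
|---|---|---|---|---|
| Segmentation | Yes, one rating per procedure | Cause: "Do you have any clue what was the origin of the unacceptable segmentation" | Not asked | Not asked |
| Registration | Yes, per scan pair | "If not acceptable level of image registration: Can it be corrected manually", plus cause, in one free-text line | Not asked (only whether it is possible) | Not asked |
| Device detection | Yes, per scan | Cause: "What is in your view the origin of the unacceptable levels of automatic device detection" | Not asked | Not asked |

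Count: failure option 3 of 3; any correction question 1 of 3; achieved correction or work-around 0 of 3; time or speed 0 of 3.

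The registration line is a single answer for a table with five rows of scan pairs. If more than one pair is poor, the answer need not be traceable to a particular pair.

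**Step 3. Other possible sources.**

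- *Free text.* The segmentation rating has a space to elaborate. All three algorithms have a question on glitches, worded for segmentation and device detection as "Did you notice/experience any glitches? If yes, please elaborate". Appendix V invites comments on software bugs at planning and at the end of the procedure. None of these prompts for a correction.
- *Times.* Appendix V Part A records start, end and total planning time, and Part C records fluoroscopy time. A delay from a segmentation failure could fall within planning time, but neither figure can be attributed to a failure or its correction.
- *Device deficiencies.* Section 8.7.9 summarises these with any corrective actions taken. However, the items that section 15.2 lists for collection are the date and whether the deficiency could have led to a serious adverse device effect. Corrective action and its duration are not listed.
- *General rules.* Section 8.3 provides counts and percentages for categorical data, but no categorical variable for correction exists to summarise.

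**Step 4. Definition.** The plan does not say what counts as quick.

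**Step 5. Scale, for context only.** The plan's total of 37 reproduces: 33 / (1 − 0.10) = 36.67, rounded up to 37. The denominator of the 5% rule is not clearly stated. If it is the 33 Per Protocol subjects, one failed case is 1/33 = 3.0% and two are 2/33 = 6.1%. With 37 the figures are 2.7% and 5.4%. On either assumption the rule tolerates one failed case and not two, so few failures would need describing if results lie near that limit.

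**The case against.** The strongest reply is that the component is not wholly lost. The questionnaire is semi-structured and the endpoint is described as partly qualitative. An operator can write down a work-around, and an outright failure may also be reported as a device deficiency. This stands in part. A reader might infer that the component will be blank for segmentation and device detection, and the documents do not support that. What remains is that, without a prompt, silence cannot be told apart from an uncorrected failure.

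A second reply is that registration is a natural place for the question. Table 4 describes a step in which the user confirms or corrects the registration, and no comparable manual step is described for the other two algorithms. The wording of 8.7.2 may simply be too broad. That is plausible, and it is why removing the component is offered as an alternative. It does not rescue the present text, which names all three algorithms and includes speed.

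Third, section 8.7 calls the secondary objectives descriptive. This limits the weight of the point, but a descriptive endpoint still needs data. Finally, the full e-CRF is not part of the documents and may hold further fields. If so, citing them in 7.1.1 and 8.7.2 would close the point.

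**Conclusion.** The point holds for the correction and work-around component only. Followed as written, the plan yields a failure percentage for all three algorithms, but no consistent record of whether failures were resolved or how fast. The gap concerns half of one of the four bullets of a descriptive secondary endpoint. No primary endpoint depends on it. It is worth fixing because it is cheap to fix, not because it threatens the study's main conclusions.

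Three stronger readings should be avoided:

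- A reader might infer from section 8.2 that the sample size depends on this component. It does not: 8.2 says the component will be evaluated, and rests the 33 on expert expectation.
- A reader might infer that the 5% rule cannot be judged without correction status. The rule does not use correction status. Because it refers to failures related to CBCT or CBCT-FS, it may not even cover segmentation on the preoperative CT.
- A reader might infer that what happened could never be reconstructed. The documents do not establish this, since comments, deficiency reports and unseen e-CRF fields may help in single cases.

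The conclusion assumes that Appendix IV as printed is the complete instrument for this endpoint, as section 7.1.1 indicates.

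**What to change.** In Appendix IV, for each of the three algorithms and beside each scan or scan pair marked *failed* (for segmentation, beside its single rating), add two fields: *Corrected or worked around during this procedure: yes / no* and *minutes added*. For segmentation, state that planning counts as part of the procedure.

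In the Analysis part of 8.7.2, list failures per algorithm as corrected or uncorrected, with the individual minutes added, beside the 5% rule. With perhaps one or two failures, a listing is more useful than a median. It also removes the need for a cut-off for quickness, although one should be defined if the word stays in the endpoint. State that subjects treated before the form change lack these fields.

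If the sponsor does not wish to collect this, remove the component from 8.7.2 and 8.2.

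The cost is two short fields, filled in only after a failure, on a form already completed after every procedure, plus one listing and a document change under section 10. The main drawback is incomplete coverage. The first patient was enrolled in October 2023 and this revision is dated June 2024, so about 8 of the planned 18 months had passed. The documents do not say how many subjects had been treated by then.

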8.7.3. Secondary objective: Quality of the Interventional plan

Objective

To determine the quality of the interventional plan (pre-procedural planning).

Endpoint

The quality of the pre-procedural plan will be determined by comparing the pre-procedural planned navigation trajectory with the actual navigation trajectory towards the first lesion.

IGT Systems	Feasibility Clinical Investigation Protocol AirWaze – easy and advanced tools for CBCT guided lung interventions	Doc ID: XCY607-130895 Rev: 04 Date: 2024-Jun-19 Page 28 of 56
-------------	--	--

Analysis

The objective will be expressed in the percentage of performed navigation trajectories that match the planned pre-procedural navigation trajectory divided by all performed navigation trajectories. The cases where the planned and performed navigation trajectories do not match, the reason for discrepancy will be presented.

8.7.4. Secondary objective: Confidence level

Objective

To assess the confidence levels of interventional pulmonologists while using AirWaze (pre-procedural planning).

Endpoint

Confidence levels of pulmonologists are defined as a score (0-10) to examine the degree of confidence of specialists regarding:

- 1) the localization of the lesion and planned navigation trajectory.
- 2) reaching the first pulmonary lesion based on the planning.

Analysis

The level of confidence is scored between 0 and 10, respectively (not confident to very confident). The analysis includes a calculation of the mean, median and standard deviation assuming a normal distribution. This objective succeeds if the mean confidence level is 6.5 or higher for both confidence level scorings. More information about the confidence level can be found in

IGT Systems	Feasibility Clinical Investigation Protocol	Doc ID: XCY607-130895
	AirWaze – easy and advanced tools for CBCT guided lung interventions	Rev: 04 Date: 2024-Jun-19 Page 29 of 56

Appendix V: AirWaze Procedural Analysis.

8.7.5. Secondary objective: Cognitive load during navigation

Objective

To assess the intraprocedural cognitive load of CBCT-guided NB.

Endpoint

The cognitive load of pulmonologists during the navigation of the first lesion will be measured with the Surgical Task Load Index (SURG-TLX) which is a validated method for measuring cognitive load, asked after tissue sampling of the first lesion ^{12,16,17}.

Analysis

The objective will be expressed in the SURG-TLX, which is a score from 0 to 300 for the complexity of the task in the procedure based on a variety of demands. The analysis includes a calculation of the mean, medians and standard deviation assuming a normal distribution. Also the individual demands will be analyzed with calculated means, medians and standard deviations. More information about the cognitive load can be found in Appendix V: AirWaze Procedural Analysis.

8.7.6. Secondary objective: Radiation exposure for patients and staff

Objective

To assess the radiation exposure for patients and staff.

Endpoint

- Radiation exposure for patients will be measured in effective dose (mSv) and DAP (Gy·cm²) per procedure including disaggregated fluoroscopy, CBCT and CBCT-FS scan dose. Also, the fluoroscopy time (minutes) will be measured.
- Radiation exposure for staff is measured in an average scattered effective dose (mSv) per procedure at hand and chest.

Analysis

- The radiation exposure for patients will be expressed in an average effective dose and DAP per procedure. The average effective dose and DAP will be higher compared to conventional procedures, but the increase in radiation dose will be relatively low (Appendix VI: Radiation Dose of CBCT-guided NB). The analysis includes a calculation of the mean, medians and standard deviations for effective dose and DAP per procedure.
- The radiation exposure for staff will be expressed in the average effective dose at hand and chest. The average effective dose and DAP will be higher compared to conventional procedures, but this increase in radiation dose will be relatively low (Appendix VI: Radiation Dose of CBCT-guided NB). The analysis includes a calculation of the mean, medians and standard deviations for effective dose at hand and chest.

